### **Maximum tolerated dose (MTD)**

The MTD for Olaparib is defined as the highest dose at which no more than 1 in 6 of the patients in the cohort experienced a DLT during the period of observation of DLTs. Conclusions of the steering committee for the definition of the MTD will be submitted to an independent committee (IDMC) before opening the expansion cohort.

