- Any other study drug related toxicity considered significant enough to be qualified as DLT in the opinion of the investigators after discussion with the sponsor.

In addition, the following events, in case they are related to the toxicity of the treatments, will also be considered as DLT:

- Interruption of radiotherapy for seven consecutive days or longer,
- Interruption of Olaparib for 14 days or longer, whether this interruption happens on consecutive days or not.

A **DLT validation committee** will be consulted before the first escalation to a new dose level (see section 12.1.2).

Maximum tolerated dose (MTD)

The MTD for Olaparib is defined as the dose at which an unacceptable frequency of DLT is observed (33%). Conclusions of the steering committee for the definition of the MTD will be submitted to an independent committee (IDMC) before opening the expansion cohort.

Recommended phase II dose (RP2D)

The RP2D dose corresponds to the dose level to be recommended for further investigations in phase II trials. The RP2D dose for Olaparib will be identified by the steering committee based on the MTD for Olaparib as defined following the dose escalation trial, as well as additional safety data, including acute and late toxicities, PK and PD data. Data from all patients (dose escalation trial and expansion cohort) will be used to define the RP2D.

3.4.DOSE ESCALATION PART

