3.4.2. Dose levels

- Dose escalation study assessing 4 dose levels of Olaparib in association with concomitant radiotherapy.

Level	-1	1	2	3	4
Olaparib	25 mg (daily)	25 mg (b.i.d)	50 mg (b.i.d)	100 mg (b.i.d)	150 mg (b.i.d)

- The starting dose of Olaparib is 25 mg b.i.d.
- The maximum dose of Olaparib administered (150 mg x 2) will not be exceeded.
- No skipping of the dose will be allowed.
- For a given patient, dose will never be escalated.
- **As long as no DLT is observed**, patients will be allocated to 4 dose levels following a 3+3 design with the following characteristics:
 - Inclusions of cohorts of 3 patients,
 - At dose levels 1 and 2, before accrual to next higher dose level, at least 2 patients with 6-week follow-up will be required,
 - At dose level 3, before accrual to dose level 4, at least 2 patients with 8-week follow-up will be required

- **As soon as the first DLT is observed**, patients will be allocated following a TITE-CRM design [Normolle et al. Statistics in Medicine 2003]. When a patient is eligible for enrollment, the probability of DLT is estimated for each dose level, based on the trial experience up to that time and the prior expectations for toxicity.
 - Each new patient is assigned to the currently estimated target dose, defined as the dose having an estimated probability of toxicity closest to but not greater than the target rate (33%), subject to the following restrictions :
 - A minimum of 2 patients will be entered on each dose level,
 - At dose levels 1 and 2, before accrual to next higher dose level, at least 2 patients with 6-week follow-up will be required,
 - At dose level 3, before accrual to next higher dose level, at least 2 patients with 8-week follow-up will be required,
 - In case of important accrual rate, to maintain operating characteristics of TITE-CRM design and patient safety, the Sponsors might decide to suspend the inclusions.
 - The prior distribution of the dose-toxicity model will be chosen to control the expected number of toxicities in the trial under a variety of scenarios about the true relationship between dose and toxicity.
 - In the TITE-CRM paradigm, patients who have been enrolled in the trial but have not experienced DLT are included in the probability calculation with a weight equal to the proportion of the 13.5-week DLT observation period they have completed; patients who experience toxicity or completed the observation period without toxicity are assigned full weight.

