10.2. DEFINITION OF STUDY POPULATIONS

Dose escalation part

- Population assessable for DLT assessment :
 - Patients assessable for the DLT assessment must fulfill all the following criteria:
 - Completed the DLT assessment period
 - Received concomitantly at least seven consecutive days of Olaparib and radiotherapy treatment (any dose) at least once.
 - Unless they develop a DLT, the following patients will not be included in the population assessable for DLT :
 - Patients who did not receive radiotherapy
 - Patients who did not receive nor Olaparib;
 - Patients who did not complete the full DLT evaluation period and goes off-treatment for reasons other than toxicity;

These patients will be replaced to reach the sample size requirement for dose escalation study.

- Safety population: patients who received radiotherapy or olaparib, at least once, irrespective of the dose. .

Expansion cohort

- Eligible population: All patients included without major violation of eligibility criteria.
- Population eligible and assessable for the primary endpoint : patients who fulfill all criteria below:
 - Eligible patients
 - Received concomitantly at least seven consecutive days of Olaparib and radiotherapy treatment (any dose) at least once.
 - at least one disease measurement recorded not less than eight weeks after treatment onset.

The following patients will also be included in the population evaluable for efficacy; they will be considered as failures for the primary endpoint (i.e. progressive disease at 6 months) and not be replaced in the efficacy analysis:

- Eligible patients withdrawn due to drug-related toxicity without any tumor assessments after the start of study treatment.
- Eligible patients withdrawn due to significant clinical deterioration of unknown reason, hypersensitivity reactions, or unrelated AEs without any tumor assessments after the start of study treatment.
- ***Replacement of patients: patients who do not comply with the definition of the population "eligible and assessable for the primary endpoint" will be replaced to reach the sample size requirement for expansion cohort.***
- Safety population: patients who receive at least one administration of Olaparib, or radiotherapy treatment at least once.

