10.3. STATISTICAL ANALYSIS

A statistical Analysis Plan (SAP) will be produced by the statistician of the study and validated by the steering committee. A preliminary version will be produced prior to the first inclusion. The SAP will be updated when necessary (Substantial modification of the protocol, IDMC recommendations, etc) and systematically validated by the steering committee.

Dose escalation part

- Dose-toxicity modeling
 - At the end of the trial, the posterior distribution of the dose-toxicity parameter α and DLT at each dose, will be estimated using the power dose-toxicity model and normal prior distribution on α used to conduct the trial.
 - 95% posterior intervals for the toxicity probabilities will be reported.
- Patient characteristics at baseline will be provided
 - Compliance with eligibility criteria,
 - Epidemiological characteristics,
 - Clinical and laboratory characteristics,
 - Treatment characteristics.
- Toxicities observed at each dose level will be recorded in terms of event type, severity, dates of beginning and end, reversibility and evolution. Data will be gathered in tables summarizing toxicities.
- Efficacy analysis: efficacy endpoints will be reported in terms of counts and proportions for each dose levels. Subgroup analyses will be conducted for metastatic and non-metastatic patients.
- All analyses will be descriptive; no p-values will be calculated.
- Data analyses will be provided by dose groups and for all study patients, combined wherever appropriate.
- For continuous variables, summary statistics will include number of patients, median, minimum, and maximum, and additional percentiles if appropriate.
- Categorical endpoints will be summarized using number of patients, frequency, percentages.
- For survival endpoints, median survival time will be reported.
- Missing data will not be imputed.

Expansion cohort

- Patient characteristics at baseline will be provided
 - Compliance with eligibility criteria,
 - Epidemiological characteristics,
 - Clinical and laboratory characteristics,
 - Treatment characteristics.
- Toxicities will be recorded in terms of event type, severity, dates of beginning and end, reversibility and evolution. Data will be gathered in tables summarizing toxicities and side effects for each dose level and cycle.
- Efficacy analysis: efficacy endpoints will be reported in terms of counts and proportions. Subgroup analyses will be conducted for metastatic and non-metastatic patients.

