
Study design
	
STUDY DESIGN
 
This is a multicenter, prospective phase Ib trial based on a dose escalation study design (3+3 traditional design) assessing four dose levels of Olaparib given with concomitant radiotherapy, followed by an expansion cohort.
 
DEFINITIONS
 
Dose-limiting toxicity (DLT)
 
A DLT is defined as an adverse event (AE) or laboratory abnormality that fulfills all the criteria below:
 
 
○ Occurs during the period of observation of DLTs defined as the period between the first day of treatment administration and up to 6 weeks after the end of radiotherapy.
 
○ Is considered to be at least possibly related to the treatment strategy (radiotherapy or Olaparib).
 
○ Is unrelated to disease, disease progression, inter-current illness, or concomitant medications.
 
○ Meets one of the criteria below, graded as outlined or according to NCI CTCAEv4.0 :             
 
▪ Any grade <math>\geq 3</math> musculoskeletal or cutaneous toxicity within the field of radiation:                 
 
• Occurring at a radiotherapy dose <math>< 30\text{Gy}</math>
 
• Occuring at a radiotherapy dose <math>\geq 30\text{Gy}</math> and without regression to a grade <math>\leq 2</math> in a time limit of 4 weeks
 
 
 
▪ Any non-hematological toxicity <math>\geq</math> grade 3 (except for nausea, vomiting, fatigue, alopecia and fever)
 
▪ Laboratory abnormality <math>\geq</math> grade 3 lasting <math>> 5</math> days (except for hyperglycaemia and changes in serum electrolytes/enzymes without clinical impact)
 
▪ Febrile neutropenia (absolute neutrophil count [ANC] <math>< 1.0 \times 10^9/\text{L}</math> and fever <math>\geq 38.5^\circ\text{C}</math>) and/or documented infection with ANC <math>< 1.0 \times 10^9/\text{L}</math>
 
 
 

- Grade 4 neutropenia (absolute neutrophil count < 500) lasting ≥ 7 days
- Grade 4 thrombocytopenia or bleeding requiring a platelet transfusion
- Any other toxicity grade ≥ 4
- Any other study drug related toxicity considered significant enough to be qualified as DLT in the opinion of the investigators after discussion with the sponsor.
- In addition, the following events in case they are related to the toxicity of the treatments will also be considered as DLT:

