#### Dose levels

- Dose escalation study assessing 4 doses level of Olaparib in association with concomitant radiotherapy.

Level	-1	1	2	3	4
Olaparib	25 mg (daily)	25 mg (b.i.d)	50 mg (b.i.d)	100 mg (b.i.d)	150 mg (b.i.d)

- The starting dose of Olaparib is 25 mg b.i.d.
- The maximum dose of Olaparib administered (150 mg x 2) will not be exceeded.
- No skipping of the dose will be allowed.
- For a given patient, dose will never be escalated.
- Patients will be allocated to 4 doses levels following a 3 + 3 design.
- A minimum of 3 patients and a maximum of 6 patients will be entered on each dose level.
- All 3 patients within a dose level will be observed during after the period of observation of DLTs before accrual to the next higher dose level may begin.
- For the dose escalation part, a DLT validation committee will be consulted at each DLT notification for validation of the DLT status ([see section 12.1.2](#)).
- Dose escalation will proceed according to the following scheme:

Number of patients with DLT at one dose level	Escalation Decision Rule
0 out of 3	Enter 3 patients at the next dose level.
$\geq 2$	Dose escalation will be stopped. This dose level will be declared as the maximum administered dose (MAD). Three additional patients will be entered at the next lowest dose level if only 3 patients were treated previously at that dose.
1 out of 3	Enter at least 3 more patients at this dose level. 
 
If 0 of these 3 patients experience DLT, proceed to the next dose level.
 
If 1 or more of this group suffer DLT, dose escalation will be stopped, and this dose is declared as the MAD. Three additional patients will be entered at the next lowest dose if only 3 patients were treated previously at that dose.
 

$\leq 1$ out of 6	This will be the maximum tolerated dose (MTD).

- As described above, the maximum administered dose (MAD) for Olaparib is the dose in which  $\geq 2/3$  or  $\geq 2/6$  patients experience DLT.
- If the MAD for Olaparib is seen at the starting dose level, then dose level "-1" will be the recommended dose.
- The MTD for Olaparib is defined as the highest dose at which no more than 1 in 6 of the patients in the cohort experienced a DLT during the period of observation of DLTs (i.e. MTD corresponds to 25% DLT). A DLT validation committee will be consulted at each DLT notification for validation of the DLT status ([see section 12.1.2](#)).

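### The SAP still describes a 3+3 escalation with an MTD of at most 1 DLT in 6 and omits the model-based DLT estimates that the protocol's 33%-target TITE-CRM requires, so reporting by the SAP can name a different MTD

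*SAP*

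**What the plan says.** **SAP.** Section 1.1 gives a "dose escalation study design (3+3 traditional design) assessing four dose levels of Olaparib", with 3 to 6 patients per level. A level with at least 2/3 or 2/6 DLTs stops escalation. On the MTD it says: "The MTD for Olaparib is defined as the highest dose at which no more than 1 in 6 of the patients" have a DLT, and under Dose levels it adds "i.e. MTD corresponds to 25% DLT". For the escalation primary endpoint, section 3.2.1.1 lists graded toxicity and DLT incidence per dose level. Section 3.1.1 and Tables 9.1 to 9.9 are descriptive counts.

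**Protocol.** Section 3.4.2 uses cohorts of three until the first DLT and a TITE-CRM afterwards. Each new patient then goes to the current target dose, "defined as the dose having an estimated probability of toxicity closest to but not greater than the target rate (33"%). Section 10.1 sets a minimum of 2 patients per level, and section 3.4.2 stops inclusion at 24 eligible and assessable patients. Section 3.3 says: "The MTD for Olaparib is defined as the dose at which an unacceptable frequency of DLT is observed (33"%). Under section 10.3, the dose-toxicity parameter and the DLT probability at each dose "will be estimated using the power dose-toxicity model and normal prior distribution", with 95% posterior intervals. The same section commits to updating the SAP after a substantial protocol modification.

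**DLT population.** Protocol 10.2 and SAP 2.1.1 exclude and replace, unless they had a DLT, "Patients who did not complete the full DLT evaluation period and goes off-treatment for reasons other than toxicity". Protocol 3.4.2 gives DLT-free patients a weight equal to the share of the 13.5-week window completed.

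**The concern.** Establishing the MTD and RP2D is the primary objective of the escalation part. The two documents differ on the design, on what the MTD is, and on the DLT rate attached to it (1 in 6 and 25% in the SAP, 33% in the protocol). The model estimate that the protocol plans for each dose has no counterpart in the SAP. A statistician reporting from the SAP would produce raw counts and, if the synopsis rule were used, could name a dose that the protocol's criterion would not.

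The SAP rule also does not fit the data that the protocol generates. Its decision table is written for levels of 3 or 6 patients, while a TITE-CRM level may hold 2, or more than 6.

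**Working it through.** **1. The sample size hides the conflict.** Protocol 10.1: six times 4 levels = 24. SAP 1.1: at most 6 per level × 4 levels = 24. Both then accrue up to 26, an allowance of 2/26 = 7.7%. The figure of 24 reproduces under either design.

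**2. The thresholds.** SAP count rule: 1/6 = 16.7%. SAP stated rate: 25%. Protocol: 33%. An observed 2/6 = 33.3% is about the protocol's target rate but is a rejection in the SAP table.

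**3. How strict the SAP rule is.** A level passes with 0/3, or with 1/3 followed by 0/3. For true DLT rate p and q = (1−p)³:

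P(pass) = q + 3p(1−p)² × q

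At p = 0.33: q = 0.3008 and 3p(1−p)² = 0.4444, so P = 0.3008 + 0.4444 × 0.3008 = **0.434**.

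| True DLT rate | P(pass 3+3) |
|---|---|
| 16.7% | 0.780 |
| 25% | 0.600 |
| 33% | 0.434 |
| 40% | 0.309 |

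If six patients are treated at a true 33%, the chance of at most 1 DLT is 0.67⁶ + 6 × 0.33 × 0.67⁵ = 0.090 + 0.267 = 0.358.

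**4. The same data under both rules.** Take 0/3, 1/6 and 2/6 at levels 1, 2 and 3.

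- SAP: level 3 has 2/6 and is rejected; level 2 has 1/6. MTD = level 2.
- Power-model CRM: DLT probability at level i = sᵢ^exp(a), with a ~ N(0, σ²), evaluated at the posterior mean of a. The chosen dose is the one closest to but not above 33%. The documents give neither skeleton (sᵢ) nor σ², so both are assumed. Four skeletons come from the indifference-interval method around 33% (half-width 0.05 or 0.08); the fifth is ad hoc.

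| Skeleton, levels 1–4 | Level 3 / level 4, σ² = 0.5 | Level 3 / level 4, σ² = 1.34 |
|---|---|---|
| 0.147, 0.233, 0.330, 0.431 | 0.28 / 0.38 | 0.27 / 0.37 |
| 0.069, 0.178, 0.330, 0.490 | 0.31 / 0.47 | 0.31 / 0.47 |
| 0.233, 0.330, 0.431, 0.527 | 0.30 / 0.40 | 0.28 / 0.38 |
| 0.015, 0.069, 0.178, 0.330 | 0.28 / 0.44 | 0.30 / 0.46 |
| ad hoc | 0.27 / 0.40 | 0.28 / 0.41 |

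Level 3 lies at 0.27 to 0.31 and level 4 at 0.37 to 0.47, so all ten settings choose **level 3**.

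**5. Where the rules need not differ.** With no DLT at any level, both reach level 4. With 0/3, 0/3, 1/6 and 2/6, the SAP gives level 3; the CRM gives level 4 in nine settings and level 3 in one. Disagreement therefore depends on the data and the prior.

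**6. Partial follow-up.** A DLT-free patient who leaves for a non-toxicity reason after 6.75 weeks has weight 6.75/13.5 = 0.5 under protocol 3.4.2. Under 10.2 the same patient is excluded and replaced. The protocol does not say which applies to the final model.

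**The case against.** The best defence is that every 3+3 statement sits in SAP section 1, which is headed as a protocol summary. Sections 2 and 3 contain no MTD rule. Protocol 3.3 and 12.1.3 give the MTD conclusion to the steering committee with IDMC review, and 10.3 refers to the model used to run the trial. Protocol 7.1.6.2 already tabulates an RP2D, so the SAP may have driven no dosing decision.

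That limits the consequence but does not remove the defect. The SAP's operative sections also lack the model. They are out of step elsewhere too: Table 9.4 lacks the lymphopenia exemption of protocol 3.3, and section 2.2 checks for inoperable tumours and 18 non-inclusion criteria against the protocol's 21. Data from all patients may still refine the RP2D (protocol 3.5).

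A reader might infer more than the documents support:

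- *That the MTD will differ.* It can; step 5 shows data where it does not.
- *That the SAP drops the primary endpoint.* It keeps DLT incidence per level; the model, posterior estimates and intervals are missing.
- *That there are four rival MTD definitions.* Protocol 3.4.2 is an allocation rule, and the SAP's 25% is a gloss on its 1-in-6 rule.
- *That the SAP's DLT population is leftover 3+3 logic.* SAP 2.1.1 follows protocol 10.2 closely, so that tension is inside the protocol.
- *That larger levels, such as ten patients, can be judged by 1 in 6.* The SAP caps levels at six, and the protocol judges by model estimate, not raw proportion.
- *That the SAP was edited after the TITE-CRM was adopted and the change ignored.* The COVID-19 section (3.3) shows a late edit, but the available text does not date the design change.

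**Conclusion.** The mismatch is explicit and bears on the primary objective. The SAP's design, MTD definition and patients-per-level text do not match the protocol, and the posterior DLT probabilities and 95% posterior intervals of protocol 10.3 are absent from the SAP.

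On size: a dose at a true 33% rate passes the SAP's 3+3 rule with probability 0.43, and one plausible data set gives level 2 under the SAP and level 3 under the CRM in all ten settings. The 0.43 is exact but measures how strict the rule is; it is not an operating characteristic of the trial as the protocol runs it. The CRM figures rest on assumed skeletons and variances, treat all follow-up as complete and ignore TITE weights, so they show direction only. The risk that remains is mainly to the final analysis and report. Nothing here shows that a wrong dose was chosen, and no target rate or dose is preferred.

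**What to change.** 1. Align the design, MTD and sample-size text of SAP 1.1 with the approved protocol.
2. Add to SAP 3.2.1.1, and to the DLT tables, the power-model posterior DLT probability and 95% posterior interval per dose level. State the skeleton and prior actually used in the trial.
3. Have the steering committee reconcile the MTD definitions (protocol 3.3 against SAP 1.1 and its 25% gloss), and state how the MTD relates to the allocation target in protocol 3.4.2.
4. Separately, reconcile protocol 10.2 with the weighting in 3.4.2, so that it is clear which patients enter the final model. This is more than wording. Weighting every DLT-free patient would override 10.2, would credit follow-up to patients who left before radiotherapy began on day 8, and would affect replacement and the count towards 24.

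The cost is a SAP revision validated by the steering committee, a model run that the protocol already requires, a short clarification of the MTD and a decision on item 4. No new data are needed for items 1 to 3.

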### **Recommended phase II dose (RP2D)**

The RP2D dose corresponds to the dose level to be recommended for further investigations in phase II trials. The RP2D dose for Olaparib will be identified by the steering committee based on the MTD for Olaparib as defined following the dose escalation trial, as well as additional safety data, including acute and late toxicities, PK and PD data. Data from all patients (dose escalation trial and expansion cohort) will be used to define the RP2D.

### **DOSE ESCALATION PART**

#### Regimen description:

Concomitant treatment by continuous Olaparib and radiotherapy.

- Olaparib will be given orally, continuously, twice a day, as appropriate for assigned dose level, from Day1 to the end of radiotherapy. Olaparib will be started one week before the start of radiotherapy and will be continued until the last day of radiotherapy. Beyond this period, Olaparib could be continued at the investigator's discretion and after sponsor authorization, until progression.
- Radiotherapy consists of fractionated focal irradiation at a dose of 1.8 Grays (Gy) per fraction given once daily five days per week (Monday through Friday), for a total dose of 59.4 Gy (ie. 33 fractions). Radiotherapy starts at D8.

#### Dose levels

- Dose escalation study assessing 4 doses level of Olaparib in association with concomitant radiotherapy.

Level	-1	1	2	3	4
Olaparib	25 mg (daily)	25 mg (b.i.d)	50 mg (b.i.d)	100 mg (b.i.d)	150 mg (b.i.d)

- The starting dose of Olaparib is 25 mg b.i.d.
- The maximum dose of Olaparib administered (150 mg x 2) will not be exceeded.
- No skipping of the dose will be allowed.
- For a given patient, dose will never be escalated.
- Patients will be allocated to 4 doses levels following a 3 + 3 design.
- A minimum of 3 patients and a maximum of 6 patients will be entered on each dose level.
- All 3 patients within a dose level will be observed during after the period of observation of DLTs before accrual to the next higher dose level may begin.
- For the dose escalation part, a DLT validation committee will be consulted at each DLT notification for validation of the DLT status ([see section 12.1.2](#)).
- Dose escalation will proceed according to the following scheme:

Number of patients with DLT at one dose level	Escalation Decision Rule
0 out of 3	Enter 3 patients at the next dose level.
$\geq 2$	Dose escalation will be stopped. This dose level will be declared as the maximum administered dose (MAD). Three additional patients will be entered at the next lowest dose level if only 3 patients were treated previously at that dose.
1 out of 3	Enter at least 3 more patients at this dose level. 
 
If 0 of these 3 patients experience DLT, proceed to the next dose level.
 
If 1 or more of this group suffer DLT, dose escalation will be stopped, and this dose is declared as the MAD. Three additional patients will be entered at the next lowest dose if only 3 patients were treated previously at that dose.
 

$\leq 1$ out of 6	This will be the maximum tolerated dose (MTD).

- As described above, the maximum administered dose (MAD) for Olaparib is the dose in which  $\geq 2/3$  or  $\geq 2/6$  patients experience DLT.
- If the MAD for Olaparib is seen at the starting dose level, then dose level "-1" will be the recommended dose.
- The MTD for Olaparib is defined as the highest dose at which no more than 1 in 6 of the patients in the cohort experienced a DLT during the period of observation of DLTs (i.e. MTD corresponds to 25% DLT). A DLT validation committee will be consulted at each DLT notification for validation of the DLT status ([see section 12.1.2](#)).

	
 
The steering committee will meet before proceeding to each dose escalation.
 
Conclusions of the steering committee for the definition of the MTD and the RP2D will be submitted to an independent committee (IDMC) before opening the expansion cohort.
 
 
EXPANSION COHORT
 
Once the MTD and the RP2D has been defined based on the dose escalation study, the expansion cohort will be opened. All patients will be treated at the RP2D of Olaparib (as defined in the escalation trial) given in association with concomitant radiotherapy with the same schedule as in the phase I trial. Following the expansion cohort, the RP2D for Olaparib may be refined by the steering committee based on the MTD and RP2D (as defined at the end of the dose escalation trial), as well as additional safety data including safety data from the expansion cohort, PK and PD data. Data from all patients (escalation + expansion) will be used to refine the RP2D.

Translational research	
For consented patients, a tumor tissue biopsy sample is required to be collected at inclusion, at Day 8 of Cycle 1 before the start of the radiotherapy and one month after the end of the radiotherapy (ie. week 12). Patients must provide additional consent for these optional tumor tissue biopsy samples.
 
 
Analysis of the tumor tissue samples may include, but not be limited to:
 
DNA extraction and sequencing in order to identify: 
 
If the patient has a mutation in BRCA1, BRCA2, or another gene in the HR repair pathway
 
If a patient has a BRCA reversion or other mutation(s) that may be associated with response or resistance to olaparib plus radiotherapy
 
 
 
DNA extraction and sequencing of single nucleotide polymorphisms (SNPs) to identify genomic scars and to determine whether genomic scarring can be used as a predictor of olaparib + radiotherapy response
 
Immunohistochemistry analysis to assess NHEJ pathway integrity, cleaved Caspase-3 and γ-H2AX staining pre- and on treatment (week 4)
 
Gene expression profiling on extracted RNA to potentially identify a signature associated with response to olaparib + radiotherapy
 

Inclusion criteria	
 
Histology: patients with soft-tissue sarcoma histologically confirmed by central review (Pr [name] team), except if the diagnosis was already confirmed by the RRePS Network,
 
Upper/Lower limb or trunk wall soft-tissue sarcoma,
 
Age ≥ 18 years,
 
Locally advanced or locally recurrent inoperable tumor, outside any previously irradiated field (inoperable status must be assessed by staff including a surgeon specialized in sarcoma),
 
Eastern Cooperative Oncology Group (ECOG) performance status ≤ 2,
 
Life expectancy ≥ 6 months,
 
At least one lesion, not previously irradiated, that can be accurately measured at baseline as ≥ 10 mm in the longest diameter (except lymph nodes which must have short axis ≥ 15 mm) with magnetic resonance imaging (MRI) and which is suitable for accurate repeated measurements,
 
Adequate hematological, renal, metabolic and hepatic function:
 

	
 
- Haemoglobin <math>\geq 9</math> g/dL and no blood transfusions in the 14 days prior to study entry
 
- Absolute neutrophil count (ANC) <math>\geq 1.5 \times 10^9/L</math>
 
- Platelets <math>\geq 100 \times 10^9/L</math>
 
- Total bilirubin <math>\leq 1.5 \times</math> upper limit of normality (ULN),
 
- Alanine aminotransferase (ALAT) or aspartate aminotransferase (ASAT) <math>\leq 2.5 \times</math> ULN,
 
- Serum creatinine <math>\leq 150 \mu\text{mol/L}</math> or creatinine clearance <math>\geq 50</math> mL/min (according to local institution) in case of serum creatinine <math>> 150 \mu\text{mol/L}</math>,
 
- TP, INR <math>\leq 1.5 \times</math> ULN
 
 
9. Women of childbearing potential must have a negative serum pregnancy test within 28 days of study treatment, confirmed prior to treatment on day 1. Female patients of child bearing potential and their partners, who are sexually active, must agree to the use of two highly effective forms of contraception in combination throughout the period of taking study treatment and for at least 1 month after last dose of study drug. Males patients, who are sexually active, must agree to the use of two highly effective forms of contraception in combination throughout the period of taking study treatment and for at least 3 month after last dose of study drug. Acceptable birth control methods are described in appendix 10. Subjects of non-childbearing potential are those who have:
 
 
• Amenorrheic for 1 year or more following cessation of exogenous hormonal treatments,
 
• LH and FSH levels in the post menopausal range for women under 50,
 
• radiation-induced oophorectomy with last menses <math>>1</math> year ago,
 
• chemotherapy-induced menopause with <math>>1</math> year interval since last menses,
 
• or surgical sterilisation (bilateral oophorectomy or hysterectomy).
 
 
10. Patient is willing and able to comply with the protocol for the duration of the study including undergoing treatment and scheduled visits and examinations including follow up,
 
11. Voluntary signed and dated written informed consent prior to any specific procedure,
 
12. Patients with a French social security in compliance with the Law relating to biomedical research (Article L.1121-11 of French Public Health Code).


Non Inclusion criteria
	
 
1. Any previous treatment with a PARP inhibitor, including Olaparib,
 
2. Patients unable to swallow orally administered medication and patients with gastrointestinal disorders likely to interfere with absorption of the study medication,
 
3. Immunocompromised patients, e.g., patients who are known to be serologically positive for human immunodeficiency virus (HIV) and are receiving antiviral therapy,
 
4. Patients with known active hepatic disease (i.e., Hepatitis B or C) due to risk of transmitting the infection through blood or other body fluids,
 
5. Patients considered a poor medical risk due to a serious, uncontrolled medical disorder, non-malignant systemic disease or active, uncontrolled infection. Examples include, but are not limited to, uncontrolled ventricular arrhythmia, recent (within 3 months) myocardial infarction, unstable spinal cord compression (untreated and unstable for at least 28 days prior to study entry), superior vena cava syndrome, extensive bilateral lung disease on
 

	
HRCT scan or any psychiatric disorder that prohibits obtaining informed consent,
 
6. Patients with uncontrolled seizures,
 
7. Men or women of childbearing potential who are not using an effective method of contraception as previously describes; women who are pregnant or breast feeding,
 
8. No prior or concurrent malignant disease diagnosed or treated in the last 2 years, except for adequately treated in situ carcinoma of the cervix, basal or squamous skin cell carcinoma, or in situ transitional bladder cell carcinoma,
 
9. Patients receiving any systemic chemotherapy, radiotherapy (except for palliative reasons), within 2 weeks from the last dose prior to study treatment (or a longer period depending on the defined characteristics of the agents used),
 
10. Concomitant use of known CYP3A4 inhibitors such as ketokonazole, itraconazole, ritonavir, indinavir, saquinavir, telithromycin, clarithromycin and nelfinavir,
 
11. Resting ECG with QTc > 470msec on 2 or more time points within a 24 hour period or family history of long QT syndrome,
 
12. Blood transfusions within 14 days prior to study start,
 
13. Patients with myelodysplastic syndrome/acute myeloid leukaemia,
 
14. Major surgery within 14 days of starting study treatment and patients must have recovered from any effects of any major surgery,
 
15. Participation to a study involving a medical or therapeutic intervention in the last 30 days,
 
16. Patient unable to follow and comply with the study procedures because of any geographical, familial, social or psychological reasons,
 
17. Previous enrollment in the present study,
 
18. Patients with a known hypersensitivity to olaparib or any of the excipients of the product.
																
Route of administration	
Olaparib will be administered per os bi-daily, as appropriate assigned dose level, during 7.5 weeks (D1 to D52). Olaparib should be started one week before the start of radiotherapy and will be continued until the last day of radiotherapy. Beyond this period, Olaparib could be continued at the investigator’s discretion and after sponsor authorization, until progression.
 
Radiotherapy consists of fractionated focal irradiation at a dose of 1.8 Grays (Gy) per fraction given once daily five days per week (Monday through Friday) over a period of 6.5 weeks, for a total dose of 59.4 Gy. Radiotherapy starts at D8.
																
Treatment schedule	
Dose escalation
 

Regimen Description	

Agent	Dose	Route	Schedule	

Olaparib	as appropriate for assigned dose level	Per os	Twice daily, continuously during 7.5 weeks	

Radiotherapy	59.4 Gy	NA	1.8 Gy per fraction given once daily five days per week (Monday to Friday) over a period of 6.5 weeks.	

	Regimen Description				Agent	Dose	Route	Schedule	Olaparib	as appropriate for assigned dose level	Per os	Twice daily, continuously during 7.5 weeks	Radiotherapy	59.4 Gy	NA	1.8 Gy per fraction given once daily five days per week (Monday to Friday) over a period of 6.5 weeks.
Regimen Description																	
Agent	Dose	Route	Schedule														
Olaparib	as appropriate for assigned dose level	Per os	Twice daily, continuously during 7.5 weeks														
Radiotherapy	59.4 Gy	NA	1.8 Gy per fraction given once daily five days per week (Monday to Friday) over a period of 6.5 weeks.														

	
Treatment consists of 7.5 weeks unless evidence of disease progression or study discontinuation (withdrawal of consent, intercurrent illness, unacceptable adverse event or any other changes rendering further treatment unacceptable, etc. see section 5.2)
 
4 dose levels :
 

Level	-1	1	2	3	4	

Olaparib	25 mg (daily)	25 mg (b.i.d)	50 mg (b.i.d)	100 mg (b.i.d)	150 mg (b.i.d)	

 
Expansion cohort: All patients will receive the same regimen with Olaparib given in association with concomitant radiotherapy at the recommended dose defined in the dose escalation cohort.
	Level	-1	1	2	3	4	Olaparib	25 mg (daily)	25 mg (b.i.d)	50 mg (b.i.d)	100 mg (b.i.d)	150 mg (b.i.d)
Level	-1	1	2	3	4								
Olaparib	25 mg (daily)	25 mg (b.i.d)	50 mg (b.i.d)	100 mg (b.i.d)	150 mg (b.i.d)								
Endpoints	
PHASE I TRIAL: DOSE ESCALATION PART
 
Primary endpoint:
 

• Toxicity graded using the common toxicity criteria from the NCI v4.0.

• Incidence rate of DLT at each dose level during treatment period up to six weeks after end of radiotherapy.

 
Secondary endpoints
 

• 6-month non-progression is defined as CR, PR or stable disease (SD, more than 24 weeks) at 6 months according to RECIST 1.1.

• 6-month objective response is defined as CR or PR at 6 months according to RECIST 1.1.

• Best objective response under treatment is defined as complete (CR) and partial response (PR) recorded from the start of study treatment until the treatment with confirmation ≥ 4 weeks after initial documentation, as per RECIST 1.1. Objective response under treatment is determined once all the data for the patient is known.

• Best response under treatment is defined as the best response (CR, PR, SD) as per RECIST 1.1 recorded from the start of the study treatment until the end of treatment taking into account any requirement for confirmation as per RECIST v1.1 criteria. It is determined once all the data for the patient is known.

• 1-year Progression-free survival (PFS): PFS is defined as the time from study treatment initiation to the first occurrence of disease progression or death (of any cause), whichever occurs first.

• 1-year Overall Survival (OS): OS is defined as the time from study treatment initiation to death (of any cause).

• Functional assessment graded using the Musculoskeletal Tumour Society Rating Scale (Enneking, 1987).

• Pharmacokinetics (PK): PK measurements expressed as the AUC, the half-life of Olaparib and concentration peak.

• Pharmacodynamics (translational research): Predictive biomarkers analysis on available archived tumor tissue and mechanisms of

												

	
action/pharmacodynamic activity on fresh biopsy (pre-treatment and week 4 of treatment).
 
EXPANSION COHORT
 
Primary Endpoint
 
 
6-month non-progression is defined as CR, PR or stable disease (SD, more than 24 weeks) at 6 months according to RECIST 1.1.
 
Disease status under treatment will be reviewed centrally by an expert radiologist.
 
Reviewed data will be used for this primary endpoint analysis.
 
 
Secondary Endpoints
 
Toxicity, 6-month objective response, objective response under treatment, best response under treatment, PK, PFS and OS as defined above for the phase I escalation study. Predictive biomarkers analysis on available archived tumor tissue and mechanisms of action/pharmacodynamic activity on fresh biopsy (pre-treatment, day 8 and week 12).

